## 6. Inclusion and exclusion criteria

We will recruit individuals with stroke for this study. Since the focus of this project is to ultimately use this device to help stroke survivors, we will recruit both young adults and older adults. Inclusion criteria includes:

- 1) age 21-80
- 2) one or more cerebral strokes
- 3) a stroke at least 6 months prior to enrollment
- 4) gait asymmetry, but able to walk independently
- 5) no evidence of uncompensated hemianopsia, tested by using Pedretti's method (Pedretti 1985)
- 6) no evidence of severe (greater than 16 in the Folstein Mini-Mental Status Exam) cognitive impairment (Folstein et al. 1975) or language dysfunction that would interfere with understanding the instructions
- 7) no evidence of neglect, tested by being asked to copy a simple drawing of a house (Gregory and Aitkin 1971)

Exclusion criteria includes:

- 1) orthopedic or pain conditions
- 2) uncontrolled seizures
- 3) metal implants (stents, clips, pacemaker)
- 4) pregnancy
- 5) any condition that makes balance unstable
- 6) require a walker to walk
- 7) uncorrected visual impairments

We will also recruit healthy individuals for this study; our target subject demographic includes healthy persons of age range between 18 to 50 with no major interlimb coordination abnormalities. The exclusion criteria includes the following from the above exclusion criteria list: 1, 2, 3, 4, 5, 6, 7, & 8.

## **7. The expected results of the research**

This study will enhance rehabilitation methods used for lower limb rehabilitation, which is currently administered with a split-belt treadmill and other traditional methods. This method aims to improve upon existing methods and to also eventually enable a home-based solution. The study results will be submitted to rehabilitation, neuroscience, and engineering publications for dissemination to researchers and clinicians who are interested in using and expanding this method.

## **10. Potential risks to the subjects**

The risks for this study are slightly higher than regular walking over ground and include the possibility of falling. The risk can be compared to walking on high-heeled shoes. To minimize this risk, subjects are wearing a gait belt and are closely guarded by an experienced physical therapist. If necessary, subjects may wear a safety harness attached to the SOLO-STEP® System (Solo-Step, Sioux Falls, SD) designed to support people in the event of a fall. As such, the combined risks associated with this study are minimal.

## **11. The potential benefits to subjects**

There is potential for subjects to improve their gait patterns, which is our hypothesis regarding this method. It may not change their gait, so there may be no benefit to subjects.

## **12. Human subjects considerations**

### **a. Description of the informed consent process**

Upon initial contact, the study coordinator will send the consent form to potential subjects when they inquire about the study. This will allow them to review the consent form without feeling rushed and will give them a better opportunity to discuss study participation with a friend or family member.

When individuals arrive to the study site, the informed consent discussion will be through a private meeting between a designated member of the research study and the potential subject.

The potential subject will be given ample time to consider their participation in the study and to ask any questions they may have. They may take it home with them if they need more time and then return to USF if they are interested in participating. If the individual agrees to participate, they will sign all informed consent documents and be given a copy to retain.

The written consent form will contain all of the elements required by the Western Institutional Review Board (WIRB) as well as adherence to all federal requirements. The primary information on the consent form will include, but is not limited to, name of sponsor, explicit study procedures, risks and benefits, subject rights, consent to use data, and study contact information. Each page will contain the most recent stamped WIRB approval printed on each page of the form. It will be written in language that is understandable to the subject. The original signed consent form will be retained in the study subject's file in a locked filing cabinet in the office of a study staff member, and stored for a period of 5-years in accordance with USF IRB policy after which time paper records will be shredded.

b. Safeguards to protect potentially vulnerable subjects

All subjects for this study will have at least normal cognitive function as described in the inclusion requirements. Care will be taken to make sure potential subjects will understand the risks and that they may not receive any benefits from this study.

c. Privacy and confidentiality

The signed consent forms will be kept confidential and stored in a secured location, while any soft data collected will be stored on a desktop computer in a USF laboratory with password protection. The data will be anonymized and combined with data from other experiments, so the data will not be identifiable throughout the study and in all reports generated from this data.

d. Compensation

Subjects will be paid \$6 plus reimbursement for travel for each completed study visit and parking passes will be provided. If they do not complete the study, they will be paid for the visits completed. They will be paid within 30 days of the end of their participation in the study.

No compensation will be provided for the healthy participants.

e. Withdraw from the research study

We will discontinue testing if the subject reports or we observe signs of discomfort or fatigue that interfere with their participation in the experiment. In any of these circumstances, the experiment will immediately stop and the subject will be compensated for his/her time. Please note that the likelihood of participants experiencing these symptoms during the experiment is not greater than in their everyday lives (e.g. during walking). Since we are performing repeated-measures statistical tests, it is essential to obtain all measures from each subject. Therefore, if a subject is unable to complete the experiment, we will remove the data from analysis. Also, if a subject requests that his/her data be withdrawn, we will delete it all electronic files from our records and destroy any paper records.

13. Data and safety monitoring plan.

The collected data will be coded so no personally identifying information will ever be attached to the data. The lookup table will be stored separately from the data. Only [name] and [name] will have access to the data and the lookup table. No one but the PI ([name]) and study staff will have access to the data used in this study. The data will be recorded to spreadsheet and/or text files. Shortly after the experiment, the data will be analyzed for completeness and integrity. It will then be copied to a remote secure server and backed up. Once a subject's experiment has been verified, it will only be looked at as part of all experiments performed in conjunction with this set of experiments, all of which will be anonymous. The analysis of the entire data set (all subjects) will occur after each experiment.

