### **4. The study design including information that is needed to answer the research questions**

The goal of this study is to test the efficacy of the Gait Enhancing Mobile Shoe (GEMS), which we hypothesize can be used to correct gait asymmetry in individuals with stroke. The study will be structured around subjects walking on the GEMS before and after which the subjects' gait is recorded and analyzed. The study design is within-subjects where each individual's gait will be compared before, during, and after the training period. There will be three phases of this research, tests on healthy individuals, a short-term training on individuals with stroke that lasts up to four

sessions and a long-term training on individuals with stroke that lasts four weeks with an initial visit prior to the start of training and two follow-up tests at one and three months.

The tests on healthy people will consist of either one or two training sessions on the GEMS and/or split-belt treadmill with one pre-screening test to evaluate subjects' gait patterns. Some of the sessions will be used to optimize the motion of the GEMS and the after-effects prior to testing on individuals with stroke. Some of the sessions will be directly compared to the split-belt treadmill.

The short-term training will consist of three training sessions performed in one week with a gait evaluation on the last day and a pretest with initial fitting of the shoe the week before. One or two of the training sessions may be replaced with training on the split-belt treadmill in place of training on the GEMS to allow for a direct comparison in the change in gait.

The long-term training will consist of four weeks of training with three training sessions performed each week. Gait evaluations will be performed the week before the first training, periodically during training (no more than once per week), and followup tests at one and three months after final training. An assessment of the subjects ability to adapt to a split-belt treadmill may be conducted at the start and/or end of the experiment to allow a direct comparison of their gait.

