To measure gait, a ProtoKinetics Zeno Walkway (ProtoKinetics, Havertown, PA) or a motion capture system will be used. The Zeno Walkway calculates the desired gait parameters after an individual walks across it. For motion capture, we will use infrared-emitting markers placed bilaterally on different parts of the body, such as the shoulder (acromion process), pelvis (iliac crest), hip (greater trochanter), knee (lateral joint space), ankle (lateral malleolus), and toe (5th metatarsal head), to record 3D position data. The motion capture system will record the movement of these markers at 120 Hz. In addition, pressure switches may be taped to the bottom of the shoes, beneath the heel and toe, to measure durations of swing and stance phases

Our main analysis will be to compare the amount of learning (i.e. deviations from symmetry post-adaptation) to normal baseline symmetry. This will be done using a repeated measures ANOVA to compare baseline gait symmetry at the start of the experiment to post-adaptation at the end of the experiment and on the 1 and 3 month follow-ups. We will quantify the amount of adaptation and the change in gait asymmetry by comparing the magnitude of step length and double support differences during baseline, at the beginning of training, during training, and after training. During a symmetric gait, step lengths on each side are the same; during an asymmetric gait, step lengths are different. These measures are standard accepted measures for measuring gait asymmetries.

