## 5. Sample size

Preliminary studies with three healthy test subjects showed statistical data that indicated that the minimum number of subjects for this study is 18 ([name] et al. 2011). We powered the t-test between pre-training and post-training data. We calculated an effect size of 0.68 for step length difference, resulting in an estimated sample size of 18 subjects. We are planning two experiments, a short-term and a long-term, so we expect to need 36 total subjects to show the necessary statistical power for each. The preliminary test with healthy subjects was approved under the Einstein Healthcare Network IRB HN4365, and other preliminary tests with healthy subjects were conducted under USF IRB Pro00001858. Similarly, for the healthy person study, we expect to need a sample size of 18 subjects.

In addition, initial testing on individuals with stroke has been approved and conducted under the Einstein Healthcare Network IRB HN4365. The protocol described here is similar, but will be performed at USF and the training will involve multiple sessions, as opposed to the earlier studies that involved a single session.

According to the 2006 American Community Survey, the percentage of females in the adult population in Hillsborough County is slightly greater than male adults (51.3% and 48.7% respectively). We have no reason to think that women and men will differ in their abilities on any of these tasks. As such, we expect to enroll approximately the same number of men and women.

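### Removing every subject who does not complete discards usable gait data and makes the result completers-only; a mixed model on all available visits avoids most of this

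*Combined protocol and SAP*

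**What the plan says.** Section 12.e covers withdrawal. It opens with the reason for stopping: "We will discontinue testing if the subject reports or we observe signs of discomfort or fatigue that interfere with their participation in the experiment". It continues: "In any of these circumstances, the experiment will immediately stop". It then gives the statistical argument, "Since we are performing repeated-measures statistical tests, it is essential to obtain all measures from each subject", and draws the rule from it: "Therefore, if a subject is unable to complete the experiment, we will remove the data from analysis". Separately, a subject may ask for their data to be deleted.

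The main analysis is in section 4: "This will be done using a repeated measures ANOVA", comparing baseline symmetry with "post-adaptation at the end of the experiment and on the 1 and 3 month follow-ups". The long-term phase is described there as four weeks of training "with an initial visit prior to the start of training and two follow-up tests at one and three months". No follow-up tests are described for the short-term or healthy phases.

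Section 5 says "We are planning two experiments, a short-term and a long-term" and sizes each at 18, called the minimum, from a pre- versus post-training t-test with an effect size of 0.68. Section 1 makes self-reported comfort on the device a second basis for judging efficacy, alongside gait coordination.

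The available text does not define completion, and gives no dropout allowance, other missing-data rule or sensitivity analysis.

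**The concern.** The rule turns a limit of one method into a reason to discard data. Classical repeated measures ANOVA needs a full row for each subject. A pre-post t-test needs two values, and a mixed model uses whatever visits exist. Removing a subject with a baseline and a post-training measurement because a later visit is missing throws away information already collected.

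The rule is also selective. Discomfort and fatigue are the named reasons for stopping, so the people removed are unlikely to be a random subset. The design is within-subjects, so the estimate rests entirely on who remains in the analysis.

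Finally, the word experiment carries more than one meaning, so two analysts could apply the rule to the same data and analyse different subjects.

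**Working it through.** **1. The plan's own figure.** Inputs from section 5: effect size d = 0.68, paired pre-post t-test, n = 18. Alpha, sidedness and target power are not stated; I assume two-sided 5% and 80%.
- Normal approximation: ((1.960 + 0.842)/0.68)² = 16.97, so 17.
- Exact noncentral t: 19.
- The plan's 18 lies between them. Exact power at n = 18 (17 df, noncentrality 0.68 × √18 = 2.885) is 77.6%.

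**2. What completing the experiment could mean.**
- *Includes the follow-ups.* Section 5 calls the whole long-term phase an experiment, section 4 describes that phase with its two follow-ups, and section 12.e asks for all measures from each subject.
- *Ends before the follow-ups.* Section 4 places post-adaptation at the experiment's end and lists the follow-ups separately.
- *A single session.* In section 12.e the experiment is what stops at once when symptoms appear.

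**3. Effect of a missed follow-up (long-term phase).**

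| Analysis | Completion includes follow-ups | Completion ends before follow-ups |
|---|---|---|
| Section 4 ANOVA | subject lost | subject lost |
| Section 5 pre-post t-test | subject lost | subject kept |

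The ANOVA loss is the same in both columns because the method itself needs the full row.

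**4. Size, with assumed miss rates.** Let m be the share missing each follow-up, with all 18 having baseline and post-training data. The share with complete rows is (1 − m)² if misses are independent and 1 − m if the same people miss both. Mean number lost = 18 × (1 − share kept). Power is averaged over a binomial number kept. The last column is the smallest enrolment whose average power is at least 77.6%.

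| m | Pattern | Share kept | Mean lost of 18 | Average pre-post power | Enrolment needed |
|---|---|---|---|---|---|
| 5% | independent | 0.9025 | 1.8 | 72.5% | 21 |
| 5% | same people | 0.95 | 0.9 | 75.1% | 19 |
| 10% | independent | 0.81 | 3.4 | 67.0% | 23 |
| 10% | same people | 0.90 | 1.8 | 72.4% | 21 |
| 15% | independent | 0.7225 | 5.0 | 61.0% | 26 |
| 15% | same people | 0.85 | 2.7 | 69.5% | 22 |

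The mean number lost applies to the ANOVA under either reading. The power and enrolment columns apply only to the pre-post t-test, and only if completion includes the follow-ups; otherwise its power stays at 77.6%. I give no ANOVA power, because the documents supply neither the within-subject correlation nor the expected follow-up effect.

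**5. Comfort.** If the rule covers comfort reports, 1, 2 or 3 subjects stopped for discomfort on the GEMS would be 1/18 = 5.6%, 2/18 = 11.1% or 3/18 = 16.7% of a phase, all absent from the comfort result. The counts are assumed.

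**The case against.** The strongest reply is that the rule sits in a paragraph about stopping for discomfort or fatigue and never mentions a missed follow-up. Section 12.d speaks of not completing the study, a different word, and section 4 ends the experiment before the follow-ups. This stands as far as it goes: a reader might infer that a missed follow-up certainly removes a subject from the pre-post comparison, and the documents do not settle that. It does not rescue the ANOVA, which loses the subject anyway.

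A reader might also infer that comfort reports are certainly deleted. The text does not say so. The reason given concerns repeated-measures tests, which section 4 ties to gait symmetry, and no comfort instrument, time point or analysis is described. Not every stop concerns the GEMS either, since fatigue is also a trigger and section 4 allows split-belt sessions. The comfort point therefore stays conditional.

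Nor do the documents support saying that the gait result is biased towards the device. They do not show whether people who stop would have changed more or less than those who finish.

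The power figures rest on assumed miss rates, alpha and sidedness, and on an effect size from preliminary work in three healthy subjects. They illustrate the cost and are not a forecast.

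It can also be said that a completers-only analysis is a legitimate stated choice, and that missing at random is not always a weaker assumption. That is a good reason to show both analyses; it does not justify discarding data already collected.

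**Conclusion.** The concern holds and should be fixed before analysis. Three parts have different standing.
- **Under any reading:** the ANOVA drops long-term subjects with a missed follow-up, and the gait result becomes completers-only, with a selective exclusion of unknown direction and size.
- **Only if completion includes the follow-ups:** usable pre-post changes are also lost. At 10% missing each follow-up, power falls by 5.2 points (77.6 − 72.4) to 10.6 points (77.6 − 67.0), on the assumptions in the working.
- **Only if the rule covers comfort reports:** people stopped for discomfort on the GEMS leave an efficacy criterion, which favours the device.

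The follow-up part concerns the long-term phase alone. Sections 8 and 9 are not in the available text, so whether lost subjects are replaced could not be checked; replacement would not restore discarded comfort reports.

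**What to change.** **Section 12.e.** Delete the sentence that all measures are essential and the removal rule after it. Suggested text: *All available measurements are analysed. Data are removed only when a subject requests it. For each phase we report how many subjects stopped, when and why.* The criteria for stopping a subject are untouched.

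**Section 4.** Replace the repeated measures ANOVA with a linear mixed model using all available visits: time point categorical, within-subject correlation modelled, small-sample degrees of freedom. Give the completers-only analysis as a sensitivity analysis, with completion defined for each phase. State that the pre-post comparison includes every subject with baseline and post-training measurements, whether or not follow-ups are missed. Name which evaluation is the long-term post-training one: the schedule lists evaluations before training, periodically during it, and at follow-up, but none explicitly at its end.

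**Comfort.** Report it for everyone who wore the GEMS, with discomfort stops on the GEMS shown against the full denominator.

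**Section 5.** Say whether 18 means enrolled or analysed.

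**Cost.** No new subjects are needed, and no new visits provided that an end-of-training evaluation is already intended. The work is revised wording, one model, one sensitivity analysis, a table of stops and a comfort line. The mixed model assumes missing at random. It cannot recover short-term subjects who stop with no later gait measurement, so that result should be labelled completers-only.

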## 1. Rationale for the study, area of current scientific concern, and why the research is needed

Hemiparesis and other impairments are a frequent and disabling consequence of stroke and can lead to asymmetric and inefficient walking patterns. Training on a split-belt treadmill, which has two separate treads driving each leg at a different speed, can correct gait asymmetries post-stroke (Reisman et al. 2005, Reisman et al. 2007). However, the effects of split-belt treadmill training only partially transfer to everyday walking over ground and extended training sessions are required to achieve long-lasting effects (Reisman et al. 2009). Our previous studies suggest that the Gait Enhancing Mobile Shoe (GEMS) that has been developed in our laboratory can be used as an alternative gait training device for people with stroke ([name], Reed, and colleagues 2011, 2011, 2012, 2013).

The GEMS (Figure 1) mimics the actions of the split-belt treadmill, but can be used during over-ground walking and in one's own home, thus enabling long-term training. This GEMS does not require any external power and is completely passive; all necessary forces are redirected from the natural forces present during walking since it utilizes the wearer's weight to generate its movements. While the movements of the GEMS are similar to the split belt treadmill, and the GEMS generates a similar aftereffect, the efficacy of this shoe in modifying the gait of an individual with stroke is not yet verified. This research aims to test the GEMS on individuals with stroke to determine if the related effects that show up on healthy subjects can benefit individuals with stroke.

In this study, we will test the efficacy of the GEMS on individuals with stroke. Efficacy will be evaluated based on the change in gait coordination and also based on subjects' self-reported comfort on the device. We predict that the GEMS will result in changes to interlimb coordination of gait. Note that this is a efficacy study, not an effectiveness or safety study of the device; this distinction is made clear in a paper by Singal et al. (2014).

[figure not shown]

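### The plan does not say that falls or stopped sessions are recorded, and the non-completer rule takes subjects who cannot tolerate the device out of the analysed set

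*Combined protocol and SAP*

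**What the plan says.** All references are to the combined protocol and SAP.

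- **Section 10** names the hazard: "The risks for this study are slightly higher than regular walking over ground and include the possibility of falling". It then lists precautions: "subjects are wearing a gait belt and are closely guarded by an experienced physical therapist", with a harness if needed. It concludes that the combined risks are minimal.
- **Section 12e** gives the stopping rule: "We will discontinue testing if the subject reports or we observe signs of discomfort or fatigue that interfere with their participation in the experiment". It does not say that the stop or its reason is written down. It then argues that repeated-measures tests need every measurement from each subject, and so "if a subject is unable to complete the experiment, we will remove the data from analysis". Deletion of files is a separate provision, for subjects who ask for it.
- **Section 13** is headed "Data and safety monitoring plan". Its content is data handling: "The data will be recorded to spreadsheet and/or text files" and "Shortly after the experiment, the data will be analyzed for completeness and integrity", plus coding, access, backup and the timing of the analysis.
- **Section 1** limits the scope: "Note that this is a efficacy study, not an effectiveness or safety study of the device". The same paragraph makes the subject's own rating of comfort part of the efficacy evaluation.
- **Section 2** says that the studies will establish whether people with stroke are able to use the device in rehabilitation. It also says that a physical therapist guards all walking.

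**The concern.** The plan identifies a hazard, has a section whose heading promises safety monitoring, and places no requirement on anyone to count the hazard. Precautions reduce falls but do not record them.

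The removal rule adds a selection problem. Discomfort and fatigue are the stated reasons for stopping a session. If the stop means that the subject cannot complete, that subject's data leave the analysis. Those who remain are, by construction, people who could tolerate the training.

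Two of the study's own aims depend on the people removed: how comfortable the device is, and whether people with stroke can use it. A report based on completers would tend to look favourable on both, whatever the truth. Section 2 presents this work as the foundation for longer training studies and for possible supervised home use, so later investigators and participants would inherit the optimistic picture.

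**Working it through.** **Step 1. Is there a record of harms anywhere in the available text?**

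| Place | What it covers | Counts falls or stops? |
|---|---|---|
| Section 4 | Step length and double support differences as gait outcomes; Timed Up and Go as a fall-risk test | No. The test scores risk and does not count events |
| Section 10 | Fall hazard and precautions | No |
| Section 12e | Stopping for discomfort or fatigue; removal of non-completers | No recording instruction |
| Section 13 | Data coding, access, storage, integrity, backup, timing | No |

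The available text passes from Section 7 to Section 10, so the statement holds only for what could be read.

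**Step 2. How much must a subject do to stay in the analysis?** The plan does not define completion. In the long-term phase (Section 4) the schedule is 4 weeks × 3 sessions = 12 sessions, plus an initial visit and follow-ups at one and three months. Read literally, a subject who misses any of these measurements is removed.

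**Step 3. Effect on the count of stops.** The only plan figure needed is the denominator, 18 subjects per experiment (Section 5). That figure can be approximately reproduced. With effect size 0.68, and assuming two-sided 5% and 80% power (neither is stated), ((1.960 + 0.842)/0.68)² = 16.98, so 17; the exact paired t-test gives 19. The present point does not depend on it.

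Let x of 18 subjects stop for intolerance and fail to complete. The values of x are assumed, since the documents give none.

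| x | True proportion x/18 | Analysed set | Such stops in analysed set |
|---|---|---|---|
| 1 | 5.6% | 17 | 0 |
| 2 | 11.1% | 16 | 0 |
| 3 | 16.7% | 15 | 0 |
| 4 | 22.2% | 14 | 0 |

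The zeros follow from the definition: a stop that ends participation cannot appear among completers.

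**Step 4. Effect on comfort.** Let p be the proportion who stop, and let C and S be the mean comfort of completers and of those who stop. The mean over everyone who started is (1 − p)C + pS. The completers' mean exceeds it by C − [(1 − p)C + pS] = p(C − S). With p from 1/18 to 4/18, the bias is 6% to 22% of the difference in comfort between the two groups. The plan names no comfort scale, so this cannot be put in scale units.

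**Step 5. Falls are different.** A fall is not a listed reason for stopping, and a subject who falls and completes is kept. Suppose falls were logged, but only completers were reported. If a proportion f fall, and fallers and non-fallers fail to complete with probabilities a and b (all assumed), the completers' fall proportion is f(1 − a) / [f(1 − a) + (1 − f)(1 − b)].

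- f = 10%, a = 50%, b = 10%: 0.05/(0.05 + 0.81) = 5.8%.
- f = 10%, a = 80%, b = 10%: 0.02/(0.02 + 0.81) = 2.4%.
- Lowest ratio to the truth among the cases tried: f = 5%, a = 80%, b = 10%: 0.01/0.865 = 1.2%, about 23% of the true rate.
- Highest: f = 20%, a = 50%, b = 10%: 0.10/0.82 = 12.2%, about 61% of the true rate.

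Under these assumptions falls are understated but do not vanish. As the plan stands, with no log required, falls among completers are not counted either.

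**The case against.** The strongest defence has four parts.

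*The removal rule concerns gait data only.* Its stated reason is the repeated-measures analysis, and it removes data from analysis while reserving deletion for subjects who request it. Payment per completed visit (Section 12d) also means that attendance must be tracked. Much of this stands. A reader might infer that the plan erases harms so that they leave no trace; the documents do not support that. Non-completers' records are not ordered destroyed, and nothing forbids reporting withdrawals. What remains is that the rule has no stated limit to gait measures, and that no separate record of harms or tolerability is planned to which the rule would not apply.

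*The study is not a safety study, and its risks are called minimal.* Both statements are in the plan. They do not cover comfort or usability, which the plan itself sets out to assess.

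*Reporting duties may exist elsewhere.* This is possible. Sections 8 and 9 could not be read, and Section 12a shows oversight by an institutional review board. Reporting single events to a board would still not by itself produce counts per subject and per session.

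*Fallers are not the ones removed.* A reader might infer that the rule selectively removes those who fell. That is plausible but not stated. The selection argument is firm for stops due to discomfort or fatigue, and only a conjecture for falls.

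**Conclusion.** The point holds in this form: the available text does not require falls or stopped sessions to be recorded or reported, and Section 12e, followed as written, takes subjects who cannot tolerate the device out of the analysed set. This biases the answers on comfort and usability and leaves falls uncounted, including those among completers.

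The size is unknown. With 1 to 4 intolerance stops among 18 (assumed), 6% to 22% of subjects are affected and a completers-only set shows none of these stops. It would be wrong to go further and say that all harm would show as zero, for example 3 of 18 in truth against 0 of 15 reported. For falls, that would require every event to occur in a non-completer, which the documents do not say.

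The missing log does not itself alter the gait result. Any selection bias in the gait comparison from the same removal rule is a separate matter. The change should be made before sessions are run, because falls and reasons for stopping are hard to reconstruct later.

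**What to change.** **Section 13.** At every GEMS and split-belt session, the guarding therapist logs any fall, any near-fall or harness catch (defined in advance), and any early stop with its reason, for everyone who starts a session. Including both training modes gives the GEMS counts a comparator.

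**Section 12e.** Limit the removal of non-completers to the repeated-measures gait analysis. Keep comfort ratings, falls, stops and reasons for withdrawal for all who started, except where a subject asks for deletion.

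**Reporting.** Give counts per subject and per session, by phase and training mode, with the number who started as the denominator.

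**Cost.** One log line per session by a therapist who is already present, and one extra table. The design, sample size, gait analysis and rules for stopping a session are unchanged.
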